**A. SPECIFIC AIMS**

---

The aim of this study is to assess the effects of *N*-acetylcysteine (NAC) on initial cessation and relapse prevention in adult cigarette smokers. Specifically, this study has the following aims: **Aim 1)** Examine the efficacy of NAC, compared to placebo, in helping smokers achieve three days of continuous abstinence; **Aim 2)** Among those who maintain initial 3-day abstinence, examine the time to relapse over the 8-week intervention between NAC and placebo groups; **Aim 3)** Assess 7-day point prevalence abstinence at the 8-week end-of-treatment study visit in order to obtain effect sizes and estimates of variability to power a randomized clinical trial.

---

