Based on the previous work conducted with NAC, two key gaps in the literature have emerged. First, additional data are needed to understand if NAC is effective in initiating abstinence. Second, is NAC effective as a relapse prevention aid, following a period of abstinence, or does it assist with both? NAC administration during abstinence may be a key feature contributing to positive results, and may also help to explain the negative results. Though this hypothesis has support, it has yet to be directly tested. These questions represent the next steps in the exploration of NAC as a pharmacotherapy for TUD, prior to large-scale evaluation and implementation of NAC among clinical populations. Therefore, this study will focus specifically on NAC as a pharmacotherapy for TUD and will evaluate NAC's influence on initial cessation and relapse prevention over 8 weeks in adult smokers.

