#### Randomization (Day 0)/Abstinence Period

Participants will return to the clinic on Day 0 to receive study medication. Participants will begin taking study medication on Day 1. Day 1 will also be when they abstain from smoking. Participants will be instructed to stop smoking no later than 11:59 pm on the night of their Day 0 visit. Participants will be reinforced contingently for abstinence from smoking on Days 1-3. Two breath CO samples per day will be taken remotely and videos will be submitted via REDCap surveys to confirm smoking status during that time (during Days 1-6 of the study). In order to monitor and confirm medication adherence during the first six days of the study, participants will also record themselves taking their morning and evening medication doses. These videos will be submitted via REDCap surveys at the same time as the CO samples are submitted. If the participant prefers to take the medication before the first prompt of the morning, they will be able to record their medication video and upload the file when completing the survey. Abstinence from smoking is defined as a breath CO of  $\leq$  6 parts per million (ppm) and/or a 50-75% reduction from the participant's average screening and Day 0 breath CO samples. Participants will continue to complete the morning reports through REDCap through the remainder of the study.

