16. **Minnesota Nicotine Withdrawal Scale (MNWS) (49):** The MNWS, a DSM IV-based instrument that assesses symptoms of nicotine withdrawal, will be used to track participants' nicotine withdrawal symptoms.

17. **Modified Cigarette Evaluation Questionnaire (mCEQ)** (50): The 12-item mCEQ assesses the reinforcing effects of smoking and contains 5 subscales (smoking satisfaction, psychological reward, enjoyment of respiratory tract sensations, craving relief, aversion).
18. **Wisconsin Predicting Patient's Relapse (WI-PREPARE)** (51): The WI-PREPARE is a 7-item scale that predicts relapse to smoking through assessment of nicotine physical dependence, environmental factors, and individual difference characteristics.
19. **UPPS-P Impulsive Behavior Scale: Short version (SUPPS-P)** (52): The SUPPS-S is a 4-point Likert scale, 20-item measure that characterizes impulsive behavior through 5 subscales.
20. **Positive and Negative Affect Scale (PANAS)** (53): This questionnaire is a self-report measure that assesses positive and negative affect through ratings on 20 adjectives (10 positive and 10 negative). Each item is rated on 5-point scale capturing affect over the past 24 hours. This assessment will also be administered at weekly clinic visits and during the three days of reinforced abstinence.

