#### Statistical Analyses

Categorical clinical and demographic variables will be assessed by chi-square tests of independence, while continuous variables will be assessed using Student's *t*-test. In addition to baseline group differences, preliminary analysis of baseline characteristics with tobacco use outcomes of interest will examine significant correlates of abstinence in the study population. Characteristics found to be significantly associated with tobacco abstinence and relapse outcomes will be included as covariates in the initial stages of model development. The primary measure of interest will be the proportion of biochemically confirmed and self-reported 3-day abstinence (defined as twice per day breath CO measures of  $\leq 6$  ppm or a 75% reduction from the participant's averaged baseline and Day 0 CO samples). The proportion of participants achieving 3-day abstinence will be compared between NAC and placebo treatment groups using logistic regression models (Specific Aim #1). Secondarily, there is great interest in determining if those who achieved 3-day abstinence under NAC treatment were less likely to relapse over the course of eight weeks compared than those who achieved abstinence under placebo treatment (Specific Aim #2). Daily smoking diary data will be used in conjunction with weekly breath CO measures to determine if and when relapse to regular smoking returned during the eight weeks of treatment with the study drug. Based on recommendations for defining treatment failure, relapse will be defined as smoking during seven consecutive days or smoking at least once over two consecutive weeks (54). This definition will account for regular and irregular smoking over the course of the eight-week intervention phase. Cox proportional hazards models will be developed to assess the efficacy of NAC in prolonging abstinence and preventing relapse. Additionally, end of study 7-day point prevalence abstinence will be assessed through the proportion of self-reported and biochemically confirmed 7-day abstinence. Biochemical confirmation for end-of-study abstinence is defined as a negative daily breath CO measures ( $\leq 6$  ppm or 75% reduction from baseline) and a negative urine cotinine measure ( $<80$  ng/mL). The main effect of NAC versus placebo on the proportion of abstinent participants will be assessed using logistic regression models. All stated models will be computed both unadjusted and adjusted for significant covariates and confounders found in the preliminary analysis. All randomized participants will be included in the primary analysis (intent-to-treat; ITT) and participants will be deemed not-abstinent at any missed visit or missing CO measure (drop-out/loss-to-follow up included). In addition to the primary ITT analyses,

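### Aim 2 compares relapse among 3-day abstainers, a group formed on treatment; the plan does not call this comparison non-randomised, fix its covariates in advance, or rank it consistently against the all-randomised analysis

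*Combined protocol and SAP*

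**What the plan says.** Section A (Specific Aims) sets Aim 2 as: "Among those who maintain initial 3-day abstinence, examine the time to relapse over the 8-week intervention between NAC and placebo groups". Statistical Analyses repeats it, with interest in "determining if those who achieved 3-day abstinence under NAC treatment were less likely to relapse over the course of eight weeks", and tags it as the second specific aim. This fits the question posed in Background and Significance: "Second, is NAC effective as a relapse prevention aid, following a period of abstinence, or does it assist with both".

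On timing, Randomization (Day 0)/Abstinence Period states: "Participants will begin taking study medication on Day 1. Day 1 will also be when they abstain from smoking".

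On the model: "Cox proportional hazards models will be developed to assess the efficacy of NAC in prolonging abstinence and preventing relapse". That sentence gives no analysis population. The general rule is "All randomized participants will be included in the primary analysis (intent-to-treat; ITT", and it does not say whether it governs the relapse model.

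On adjustment: "Characteristics found to be significantly associated with tobacco abstinence and relapse outcomes will be included as covariates in the initial stages of model development". All models are run both unadjusted and adjusted, but no covariate is named. Baseline Screening Assessments already includes a suitable candidate: "The WI-PREPARE is a 7-item scale that predicts relapse to smoking through assessment of nicotine physical dependence".

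Power and Sample Size gives detectable relapse rates for all 110 randomised participants first and then, as a second step, for abstainers only. It assumes 3-day abstinence of 30% (placebo) and 50% (NAC), or 50% and 75%.

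**The concern.** Days 1-3 abstinence is the Aim 1 outcome, measured on study drug. If NAC works on Aim 1, the NAC abstainers include people who would have smoked on placebo, and the placebo abstainers have no matching group. A difference in relapse between the two sets of abstainers can then reflect who got in, what the drug does afterwards, or both.

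This matters because section E.4 says the trial should tell clinicians whether NAC helps initial cessation, relapse prevention, or both. The abstainer model addresses relapse after quitting but is not a randomised comparison. The all-randomised model is randomised but mixes cessation with relapse. The plan does not say what each can show, and the two parts of section D rank them differently. Leaving the covariates to significance testing also leaves the adjusted subset model open until the outcome data have been seen.

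**Working it through.** **Plan's own figures.** With 55 per arm, the abstinence assumptions give 16.5 + 27.5 = 44 abstainers (plan: 45) and 27.5 + 41.25 = 68.75 (plan: 70). The subset columns of Table 1 can be reproduced. With arm sizes 17/28 and 28/42, HR = ln(1 - placebo rate)/ln(1 - NAC rate), Freedman's formula with unequal allocation, 80% power and one-sided 5%, I get 2.91/2.60/2.35 and 2.25/2.09/1.95 (plan: 2.91/2.60/2.36 and 2.25/2.09/1.95). The plan does not state sidedness. At two-sided 5% the same effects have about 70% power.

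Below, hazard ratios are NAC/placebo, so they are inverted relative to Table 1.

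**Share of NAC abstainers without a placebo counterpart**, assuming NAC stops no one from abstaining:

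f = (pN - pP)/pN
- Low abstinence: (0.50 - 0.30)/0.50 = 0.40
- High abstinence: (0.75 - 0.50)/0.75 = 0.33

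This share would have to be estimated. With 55 per arm, its approximate 95% interval (log risk ratio) is 0.03-0.63 in the low case and 0.10-0.51 in the high case.

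**Apparent effect when NAC has no effect on relapse.** Placebo relapse RP = 0.80 is the middle row of Table 1. The relapse rate RE of the extra abstainers is my assumption; the documents give none.

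RN = (1 - f)·RP + f·RE; HR = ln(1 - RN)/ln(1 - RP)

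| RE | RN low / high | HR low / high | Events low / high | Bias in SE of log HR, low / high |
|---|---|---|---|---|
| 0.70 | 0.760 / 0.767 | 0.89 / 0.90 | 34.1 / 53.6 | -0.34 / -0.36 |
| 0.80 | 0.800 / 0.800 | 1.00 / 1.00 | 35.2 / 55.0 | 0 / 0 |
| 0.90 | 0.840 / 0.833 | 1.14 / 1.11 | 36.3 / 56.4 | +0.38 / +0.39 |

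The SE is the square root of (1/placebo events + 1/NAC events), about 0.35 (low) and 0.28 (high).

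**Error rate.** Simulation with exponential relapse over 53 days, daily log-rank test, two-sided 5% and 8,000 runs gave 5.2-5.4% rejection without selection. It gave 6.7-6.8% with RE at 0.70 or 0.90.

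**Direction.** A different illustration uses a latent readiness trait that drives both abstinence and relapse, again with assumed strengths. It gave subset HRs of 1.03-1.17 and 5.1-9.0% rejection, a bias against NAC. The table above allows either sign.

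**Borderline result.** At RP = 0.80, a subset result with p = 0.05 in favour of NAC corresponds to RN = 0.535 (low) or 0.596 (high). If the extras relapse 10 points less than the other NAC abstainers, those others relapse at RN + 0.1f = 0.575 or 0.629, and p becomes about 0.10. If the extras relapse 10 points more, p becomes about 0.02. Both treat f as known.

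**Large result.** The RE needed for selection alone to produce Table 1's detectable NAC rate is (RN - (1 - f)·RP)/f.
- 70% row: negative, so impossible, in both scenarios.
- 80% row: (0.46 - 0.48)/0.40 = -0.05, impossible; (0.54 - 0.533)/0.333 = 0.02.
- 90% row: (0.62 - 0.54)/0.40 = 0.20; (0.69 - 0.60)/0.333 = 0.27.

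**Events available for adjustment at Table 1's effects.**
- Low, 70% row: 16.5×0.70 + 27.5×0.34 = 20.9
- Low, 80% row: 16.5×0.80 + 27.5×0.46 = 25.9
- High, 80% row: 27.5×0.80 + 41.25×0.54 = 44.3

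In the two low cells, treatment plus one covariate leaves 10.5-12.9 events per parameter, plus two 7.0-8.6, and plus three 5.2-6.5. With three in the high cell it is about 11.

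**Significance as a filter.** For a 50/50 baseline factor with an assumed relapse HR of 1.5, z = √(E×0.25)·ln(1.5). With 35.2 to 55 events it reaches two-sided 5% only 22-32% of the time. The plan also screens on association with abstinence, which this figure does not cover.

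**The case against.** Several points on the other side stand. The plan does adjust: every model is run unadjusted and adjusted. It sets an all-randomised primary analysis, shows both relapse populations in Table 1, and describes itself as largely a source of preliminary data. The bias is small on my own figures, and it rests on relapse rates that no document supplies.

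A reader might infer that the plan never says which population answers Aim 2. The documents do not support that. Specific Aims and Statistical Analyses both name the 3-day abstainers, and the Cox sentence follows closely on that question. What remains is that the power section orders the populations the other way round and the Cox sentence names neither.

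A reader might also infer that selection would flatter NAC, or could explain an effect of the size the trial is powered for. Neither follows. The direction is unknown, and at 70-80% placebo relapse selection alone essentially cannot produce Table 1's effects.

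What the objection does not answer: the extra modified-ITT, per-protocol and completer analyses do not deal with selection into the abstainer group. The preliminary character of the study sits beside a claim of adequate power for the first two aims.

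**Conclusion.** The concern holds in a limited form. The abstainer comparison for Aim 2 is selected on a post-randomisation, on-treatment outcome that the plan expects to differ by arm. The plan does not say that randomisation fails to protect it, its covariates are left to significance in the trial's data, and section D needs reconciling on which relapse model uses which population.

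The size is modest: a subset HR of about 0.89-1.14 under no true effect, and about 6.7-6.8% two-sided error instead of about 5%. This assumes 80% placebo relapse, extra abstainers relapsing 10 points either side, NAC stopping no one from abstaining, exponential relapse and a two-sided test. It is worth correcting because it could change the reading of a borderline subset result and the correction is cheap. It does not invalidate the trial or the all-randomised analysis.

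**What to change.** 1. In Statistical Analyses and in Power and Sample Size, name the population of each relapse Cox model and make the two sections agree before unblinding. State that the all-randomised model is the randomised comparison, of cessation and relapse combined, and that the abstainer model is non-randomised. Which one leads is for the sponsor to decide.
2. For the abstainer model, replace significance-based selection with a short prespecified list drawn from baseline measures already collected, such as the FTND or WI-PREPARE, baseline CO and cigarettes per day. Size the list to the expected events: perhaps one or two covariates with about 21-26 events (low abstinence), with room for more at about 44.
3. Base no relapse-prevention claim on the abstainer result alone.

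Optional: a sensitivity analysis that varies the relapse rate of the extra NAC abstainers. It must state that it assumes NAC stops no one from abstaining, carry the uncertainty in the extra share, and be used only if observed 3-day abstinence is higher on NAC.

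Cost: a few sentences and a fixed covariate list, with no new data, visits or participants. The downside is a more cautious Aim 2 conclusion and slightly more analysis work. Adjustment reduces only measured differences, so the label in item 1 is needed in any case.

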
additional exploratory approaches (e.g., modified ITT models, per protocol analysis, and completer analysis) will be undertaken as indicated and a sensitivity analysis comparing these models to the ITT model will be completed.

**Power and Sample Size.** This study is largely focused on obtaining preliminary data to inform and power a larger randomized controlled trial to assess NAC for TUD. However, the proposed sample size (N=110) of this study will allow for adequate power to detect differences between treatment groups for the first two stated aims and hypotheses. This study is powered to assess the hypothesis that NAC, as compared to placebo, will promote greater abstinence from smoking during a 3-day quit attempt at the beginning of an eight week randomized controlled trial. In a pilot trial (N=16) investigating NAC as a cessation aid over three days of reinforced abstinence, [name] and colleagues (35) found that the majority of study participants given NAC achieved high rates of abstinence on the second and third days of reinforced abstinence (75% and 100%, respectively) following a target quit date. Conversely, those randomized to the placebo condition achieved lower rates of abstinence on the second and third days (12.5% and 25%, respectively). With a proposed sample size in the current study of 110 participants (55 randomized to each treatment assignment), this number will provide sufficient power (80%) with a type 1 error rate of 5% to detect abstinence rate differences of as low as 20% between those randomized to NAC versus placebo.

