Following the initial 3-day reinforced quit attempt, relapse rates will be examined to determine if NAC aids in relapse prevention as compared to placebo. Detectable relapse rates and associated hazard ratios (HR) based on the proposed sample size (N=110) are shown below in Table 1 based on varying relapse rates among the placebo and NAC groups. Including all randomized participants and assuming 70-90% of those randomized to placebo will relapse throughout the duration of the study, we will be sufficiently powered to detect relapse rates as high as 46-73% in those randomized to NAC (HR=1.8-2.0). Secondarily, we will assess relapse prevention among only those participants who achieved initial abstinence during the initial 3-day period. Assuming 30% of those randomized to placebo and 50% of those randomized to NAC will attain initial abstinence (low initial abstinence); we will have adequate power to detect relapse rates as high as 34-62% (HR=2.4-2.9) in the NAC group (assuming 70-90% relapse in the placebo group). If we achieve 50% and 75% initial 3-day abstinence in the placebo and NAC groups (high initial abstinence), we will have adequate power to detect relapse rates as high as 41-69% (HR=2.3-2.9) in the NAC group.

Placebo Relapse Rate	All Randomized Participants		Participants who achieve three day abstinence (ABS)			
	N=110		Low 3 day ABS; n=45		High 3 day ABS; n=70	
	Detectable NAC Relapse Rates	HR	Detectable NAC Relapse Rates	HR	Detectable NAC Relapse Rates	HR
70%	46%	1.98	34%	2.91	41%	2.25
80%	58%	1.86	46%	2.60	54%	2.09
90%	73%	1.76	62%	2.36	69%	1.95

*Table 1. Detectable rates of relapse and associated hazard ratios (HR).*

Additionally, assuming a conservative study attrition rate of 20%, a randomized sample of 110 participants (88 study completers) will provide sufficient power to detect a 23-29% difference in end-of-treatment (Week 8) abstinence between the two groups (assuming 10-30% abstinence rate in the placebo group). Therefore, 110 randomized participants will provide sufficient power to detect treatment differences for the first two stated hypotheses, and will provide effect sizes and estimates of variability for end-of-treatment abstinence at eight weeks to power a larger randomized controlled trial.

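### With 55 per arm, power for a 20-point difference in 3-day abstinence is about 57% at the plan's own 30% vs 50% scenario, not the stated 80%

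*Combined protocol and SAP*

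**What the plan says.** All of the following stands in section D of the combined protocol and SAP, under Statistical Analyses and its Power and Sample Size part.

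- **Primary outcome.** The proportion abstinent over the three reinforced days is compared between arms by logistic regression. All randomized participants are analysed, and a missing CO reading counts as not abstinent.
- **Power claim for Aim 1.** The sample is "110 participants (55 randomized to each treatment assignment"). The text says that this gives "sufficient power (80%) with a type 1 error rate of 5% to detect abstinence rate differences of as low as 20" percentage points between the arms. No placebo rate is attached and the sidedness is not given.
- **Assumed rates for the same outcome.** The relapse paragraph has a low scenario, "Assuming 30% of those randomized to placebo and 50% of those randomized to NAC will attain initial abstinence", and a high one, "If we achieve 50% and 75% initial 3-day abstinence in the placebo and NAC groups (high initial abstinence").
- **Week 8 figure.** With 20% attrition (88 completers) and 10-30% placebo abstinence, the sample "will provide sufficient power to detect a 23-29% difference in end-of-treatment (Week 8) abstinence between the two groups".
- **Overall claim.** The section says that power is adequate for the first two aims, without condition.

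**The concern.** The power to detect a given difference between two proportions depends on where the proportions lie, so a 20-point claim without a placebo rate cannot be checked as written. Where the plan does give rates for 3-day abstinence, its low scenario is a 20-point difference in the middle of the scale, where binomial variance is near its largest. 55 per arm looks too few there.

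The Week 8 figure points the same way. If 44 per arm can detect 23-29 points, 55 per arm should detect roughly 21-26 points, not 20.

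This is the only numerical support for the statement that Aim 1 is adequately powered. If it is too favourable, a null result could be taken to exclude a 20-point effect that the trial had little better than an even chance of finding. The larger trial that this study is meant to inform could inherit that reading.

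**Working it through.** **Inputs.** From the Power and Sample Size text: n = 55 per arm, type I error 5%, stated power 80%, difference 0.20, scenarios 30% vs 50% and 50% vs 75%, and pilot placebo rates of 12.5% (second day) and 25% (third day). Because missing counts as not abstinent, all 55 per arm enter the analysis and no attrition adjustment is needed. Two-sided testing is assumed, and one-sided is also tried.

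**Formula.** Pooled-variance normal approximation, with p̄ the mean of p₁ and p₂ and d their difference:

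power = Φ{ [ d√n − z√(2p̄(1−p̄)) ] / √(p₁(1−p₁) + p₂(1−p₂)) }, with z = 1.960 two-sided.

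**Step 1: when does the plan's 80% come out?** Fixing d = 0.20 and n = 55 and solving for the placebo rate gives 7.3%. By symmetry, a NAC rate of about 92.7% does the same. Between these limits, power is below 80%.

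**Step 2: the plan's scenarios.**

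- 30% vs 50%: d√n = 0.20 × 7.416 = 1.483. z√(2 × 0.40 × 0.60) = 1.960 × 0.6928 = 1.358. Denominator √(0.21 + 0.25) = 0.6782. (1.483 − 1.358)/0.6782 = 0.185, and Φ(0.185) = **57.3%**.
- 50% vs 75%: d√n = 1.854. z√(2 × 0.625 × 0.375) = 1.342. Denominator √(0.25 + 0.1875) = 0.6614. (1.854 − 1.342)/0.6614 = 0.774, and Φ(0.774) = **78.1%**.
- Sample size for 80% at 30% vs 50%: (1.358 + 0.8416 × 0.6782)² / 0.20² = 1.929²/0.04 = **93 per arm**.

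**Step 3: other placebo rates, 55 per arm.**

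| Placebo rate | Power for +20 points, two-sided | Power for +20 points, one-sided | Difference detectable at 80%, two-sided |
|---|---|---|---|
| 10% | 75.3% | 84.4% | 21.4 points |
| 12.5% | 71.5% | 81.4% | 22.5 |
| 20% | 63.2% | 74.5% | 24.7 |
| 25% | 59.7% | 71.5% | 25.6 |
| 30% | 57.3% | 69.4% | 26.2 |
| 40% | 55.6% | 67.8% | 26.4 |
| 50% | 57.3% | 69.4% | 25.5 |

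**Step 4: other methods at 30% vs 50%, two-sided.** Unpooled variance 59.0%, arcsine 57.8%, exact enumeration of the chi-square test 57.6%, logistic Wald test 56.4%, Fisher's exact test 49.1%. None comes near 80%.

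**Step 5: comparison with the Week 8 figure.** With 44 per arm, the same two-sided formula gives detectable differences of 24.5 points at 10% placebo and 29.3 at 30%, close to the plan's 23-29. One-sided it gives 21.2 and 25.9, which does not fit. Scaling the plan's own range by √(44/55) = 0.894 gives 20.6-25.9 points for 55 per arm.

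**Step 6: over-enrolment.** With 60 per arm, 30% vs 50% has 61.1%. The placebo rate at which 20 points reaches 80% moves only to 9.3%.

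**The case against.** The strongest defence is that the wording describes the smallest detectable difference under favourable conditions, as the Week 8 range does across placebo rates. At a 10% placebo rate the detectable difference is 21.4 points, and with 60 per arm it is 20.3, so the sentence is nearly right for low placebo rates. The pilot does not exclude such a rate. Its 12.5% and 25% are single-day figures, and continuous 3-day abstinence cannot exceed the lower of them. The 30% vs 50% pair was introduced to size the relapse analysis rather than Aim 1. The high scenario is close to nominal at 78%, and passes 80% (81.6%) with 60 per arm. Finally, a one-sided test at 12.5% placebo gives 81.4%, and the study describes itself as largely preliminary.

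Part of this stands. The claim is true at very low placebo rates, and the pilot figures are not 3-day rates. But the plan never states a rate near 7%. Even 12.5% gives only 71.5% two-sided. Assuming 30-50% placebo abstinence for Aim 2 while relying on about 7% for Aim 1 is inconsistent, because the outcome is the same. The high scenario is a 25-point difference and so does not support a 20-point claim. One-sided testing is not stated and does not fit the Week 8 range. The extra ten participants are meant to cover data integrity problems, so they cannot be fully credited as added power. The preliminary character of the study does not excuse a specific 80% figure for the primary outcome.

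**Conclusion.** The stated power does not hold at either 3-day abstinence scenario that the plan assumes. For a 20-point difference at 30% vs 50%, it is about 57% rather than 80%, so such an effect would be missed about 43% of the time. At placebo rates of 20-50%, the difference detectable with 80% power is about 25-26 points.

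This rests on 55 analysed per arm and a two-sided 5% test. The two-sided reading is an inference from the Week 8 range, but the conclusion at 30% vs 50% does not depend on it, since one-sided power is 69%. The claim would be correct only with a placebo rate of about 7% or lower, or a NAC rate of about 93% or higher.

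**What to change.** Replace the Aim 1 power sentence with one tied to placebo rates and sidedness, for example: *With 55 per arm, a two-sided 5% test and 80% power, the detectable difference in 3-day abstinence is about 21 points at a placebo rate of 10%, 25 at 20%, 26 at 30-40% and 25.5 at 50%. Power is 57% for 30% vs 50% and 78% for 50% vs 75%.* If a very low placebo rate or a one-sided test was intended, state it, justify it, and reconcile it with the rates used for the relapse calculation. Qualify in the same way both statements that the sample is adequate for the first two aims, as far as they concern Aim 1.

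The cost is a text edit and a less favourable stated figure. Outcome, analysis and sample size stay as they are.

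### The all-randomised time-to-relapse comparison mixes failure to quit with relapse, so it should be labelled treatment failure and reconciled with Aim 2

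*Combined protocol and SAP*

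**What the plan says.** Section A (Specific Aims) restricts Aim 2 to people who got through the quit attempt: "Among those who maintain initial 3-day abstinence, examine the time to relapse over the 8-week intervention between NAC and placebo groups". The Statistical Analyses text repeats this, describing the interest as "determining if those who achieved 3-day abstinence under NAC treatment were less likely to relapse over the course of eight weeks". In the same paragraph, "relapse will be defined as smoking during seven consecutive days or smoking at least once over two consecutive weeks". That definition does not require the participant to have stopped first. Cox models are named, but neither their population nor their time origin is given.

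The Power and Sample Size text takes a different order. After the quit attempt, "relapse rates will be examined to determine if NAC aids in relapse prevention as compared to placebo". The first population listed is everyone: "Including all randomized participants and assuming 70-90% of those randomized to placebo will relapse throughout the duration of the study". Abstainers come next: "Secondarily, we will assess relapse prevention among only those participants who achieved initial abstinence during the initial 3-day period". Two quit-rate scenarios are used. The low one reads "Assuming 30% of those randomized to placebo and 50% of those randomized to NAC will attain initial abstinence"; the high one is 50% on placebo and 75% on NAC. Table 1 applies placebo relapse rates of 70, 80 and 90% to all three of its columns: all randomised (N=110), low abstinence (n=45) and high abstinence (n=70).

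**The concern.** The trial sets out to learn whether NAC is a cessation aid, a relapse-prevention aid, or both (Section E.4; the same two gaps are set out in Section B). That requires analyses that keep the two effects apart.

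Applied literally to all 110 participants, the relapse definition makes a person who never stops smoking an event once seven smoking days have accrued. By the plan's own assumptions, 50-70% of placebo and 25-50% of NAC participants fail the 3-day attempt. Those among them who simply keep smoking have already been counted as failures under Aim 1, and would be counted again here as relapses. If NAC helped people only through Days 1-3, this analysis could still favour NAC, and the text presents it as informing relapse prevention. The results are meant to inform a larger trial, so a wrong answer of *both* could misdirect its design.

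**Working it through.** **1. Reproduce Table 1, all-randomised column.** With HR = ln(1 - p_placebo) / ln(1 - p_NAC):

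| Placebo | NAC | HR recomputed | HR stated |
|---|---|---|---|
| 70% | 46% | ln 0.30 / ln 0.54 = 1.954 | 1.98 |
| 80% | 58% | ln 0.20 / ln 0.42 = 1.855 | 1.86 |
| 90% | 73% | ln 0.10 / ln 0.27 = 1.759 | 1.76 |

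These agree within rounding of the NAC rates. The column is an ordinary proportional-hazards calculation and does not separate never-quitters from quitters.

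**2. What the all-randomised relapse rate contains.** Let A be the 3-day abstinence proportion and r the relapse proportion among abstainers. If every 3-day failure is an event, all-randomised relapse = 1 - A(1 - r). For placebo, with r = 70, 80, 90%:

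- A = 30%: 91, 94, 97%
- A = 50%: 85, 90, 95%

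In each case the result exceeds r, so no row of Table 1 can describe both all randomised participants and abstainers under this coding. At A = 30%, an all-randomised placebo rate of 70% would require no relapse at all among quitters.

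Initial failures as a share of placebo events are (1 - A) / [1 - A(1 - r)]. This is 72-77% for A = 30% and 53-59% for A = 50%. Both ranges are upper ends, because they assume that every 3-day failure carries straight on smoking.

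**3. How a pure cessation effect enters.** If r is equal in the two arms, the ratio of non-relapse proportions (NAC to placebo) is A_NAC / A_placebo. Table 1's detectable rates correspond to ratios of 0.54/0.30 = 1.8, 0.42/0.20 = 2.1 and 0.27/0.10 = 2.7. The plan's assumed quit rates give 0.50/0.30 = 1.67 and 0.75/0.50 = 1.5. A cessation effect alone therefore pushes the comparison towards Table 1's detectable range, without reaching it.

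**4. Simulation with no relapse-prevention effect.** Inputs from the plan: 55 per arm; 3-day abstinence 30% vs 50%, or 50% vs 75%; relapse among abstainers 70, 80 or 90% by Day 56, the same in both arms. Assumptions: exponential relapse after Day 3, no dropout, Cox model with Efron ties, rejection at z beyond 1.96 in NAC's favour. A stated fraction of 3-day failures has the event at Day 7, and the rest relapse like quitters.

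| 3-day failures that are events at Day 7 | Trials significantly favouring NAC |
|---|---|
| 100% | about 27-42% |
| 80% | about 16-27% |
| 50% | about 8-12% |

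The ranges run over the six settings. At 500 trials per setting, the standard error near 35% is √(0.35 × 0.65 / 500) = 2.1 percentage points, so the end points are approximate. In the 50% row the median placebo:NAC hazard ratio is only 1.11-1.18. A log-rank test in place of Cox lowers the top row to about 21-32%.

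**5. Abstainers only.** Under the same null, with r = 70-90%, the abstainers-only log-rank comparison rejects in 5-6% of trials (two-sided), close to nominal. This assumes that quitters in the two arms are alike, which randomisation does not guarantee.

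**The case against.** The strongest reply is that Aim 2 is not the all-randomised analysis. Both places that define the aim restrict it to 3-day abstainers, and that analysis is planned. All-randomised relapse appears only in the power text, and the intent-to-treat sentence refers to the primary analysis, whose endpoint is 3-day abstinence. A reader might infer that the trial would report a cessation effect as relapse prevention; the documents do not say that. What stands is that the power text puts a different population first for the same question, and that nothing says which result answers it.

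Second, the coding of never-quitters is inferred. No sentence calls an initial failure a relapse, and the power text's reference to the period after the quit attempt can be read as presupposing a quit. The poor fit with Table 1 in step 2 may mean the authors did not intend to count every failure. That is a reason to state the rule; it does not settle it.

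Third, failing the 3-day test is not the same as never quitting. One missing CO sample, or one high reading among the six, is enough to fail, and such a person may stop by Day 4. This stands, and it is why the 100% row is an upper case. The documents do not give the true fraction.

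Fourth, a reader might set 27-42% against 2.5% and infer an inflated type I error. That is not supported. In these simulations NAC does reduce the composite of not quitting or relapsing, so the rejections are correct for the comparison made. The risk lies in the name given to the result.

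**Conclusion.** Wrong as written, of modest severity because Aim 2 is secondary. Under the written definition, the all-randomised hazard ratio is a joint effect on quitting and staying quit, and it cannot by itself show relapse prevention. With the plan's rates and no effect after Day 3, it would point to NAC in anything from about 8% to about 42% of trials, depending mainly on how many 3-day failures smoke straight through. The figures also depend on dating those events at Day 7, exponential relapse among quitters, the choice of Cox over log-rank, and no dropout (the plan itself allows 20% attrition in its end-of-treatment calculation). Two conclusions do not depend on the simulation: the power text and Aim 2 lead with different populations, and Table 1's shared placebo rates cannot hold for both populations if every 3-day failure counts as an event.

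**What to change.** In the Statistical Analyses and Power and Sample Size text:

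1. State the time origin for the Cox models and how participants who fail the 3-day attempt are coded.
2. Label the all-randomised analysis, and its Table 1 column, *time to treatment failure (failure to quit or relapse)*. Say that it is a valid randomised comparison of the joint effect and is not on its own evidence of relapse prevention.
3. Present it beside the two components already planned: the 3-day abstinence difference and the abstainers-only relapse analysis. Note that the abstainer subset is selected after randomisation, so the arms may differ within it.
4. Reconcile the order of populations in the power text with Aim 2, and give the all-randomised column of Table 1 placebo rates consistent with the coding chosen.

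The cost is wording and a revised table column, with no new data, visits or participants. The real concession is that the analysis with the larger sample can no longer be called a test of relapse prevention. That question then rests on 45-70 abstainers, where Table 1's detectable hazard ratios are 1.95-2.91, against 1.76-1.98 for all randomised.
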